1.0 Objectives

The goal of this proposal is to test the hypothesis that consumption of watercress, a rich source of the cancer chemopreventive agent 2-phenethyl isothiocyanate (PEITC), will enhance the detoxification of multiple environmental toxicants and carcinogens, particularly in subjects who are null for *glutathione-S-transferase M1 (GSTM1)*, *glutathione-S-transferase T1 (GSTT1)*, or both. If our hypothesis is supported by the results of the trial, watercress could emerge as an inexpensive and plentiful dietary constituent which could promote good health by decreasing the effects of environmental stressors.

We and others have carried out extensive studies on the efficacy and mechanisms of PEITC in the context of cancer chemoprevention [1-21]. Our studies focused on the potential use of PEITC in prevention of lung cancer in smokers, as we have demonstrated that PEITC is a powerful inhibitor of lung carcinogenesis in rats and mice treated with the tobacco-specific lung carcinogen 4-(methylnitrosamino)-1-(3-pyridyl)-1-butanone (NNK) [2,20]. These studies led to a clinical trial of PEITC with the goal of determining whether it could inhibit the metabolic activation of NNK, as observed in rats and mice [11]. The results of that trial demonstrated a modest but significant effect of PEITC in decreasing the metabolic activation of NNK in cigarette smokers [11].

Unexpectedly however, PEITC showed far greater effects on the detoxification of benzene, acrolein, and crotonaldehyde in subjects who were null for *GSTM1*, *GSTT1*, or both [21] (see Preliminary Results). We now wish to extend these exciting results and assess the effects of watercress, as an abundant source of PEITC as well as other isothiocyanates, on the detoxification of environmental toxicants and carcinogens in a trial that will recruit *both* non-smokers and smokers in proportion to their prevalence in the Minnesota population. All humans are exposed to benzene, acrolein, crotonaldehyde and other related toxicants and carcinogens through their diet, polluted air, and/or endogenous metabolic sources.

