^a 1, Carcinogenic to humans; 2A, probably carcinogenic to humans; 2B, possibly carcinogenic to humans; 3, not classifiable as to its carcinogenicity to humans

^b Evaluated before evidence of its selective binding at p53 hotspots

^c Evaluated prior to evidence of its occurrence in certain foods

As described under “Preliminary Studies”, we have observed a significant enhancing effect of PEITC consumption on the detoxification of benzene and acrolein, as determined by analysis of their urinary mercapturic acids SPMA and 3-HPMA [21]. The observed effects were particularly strong in subjects lacking the *GSTM1* or *GSTT1* genes, or both, and were also observed for detoxification of crotonaldehyde

PROTOCOL TITLE: Watercress in Detoxification of Environmental Toxicants and Carcinogens

VERSION DATE: July 23, 2020

(as determined by HMPMA in urine) in these individuals. Similar results were obtained in a clinical trial of a “broccoli sprouts tea” beverage, rich in the isothiocyanate sulforaphane, carried out in China by the Kensler group [33]. In that study, in which the urinary mercapturic acid analyses were performed by our laboratory, rapid and sustained statistically significant increases in the levels of excretion of SPMA from benzene (61% increase) and 3-HPMA from acrolein (23% increase) were observed, although there was no statistical effect of *GSTM1* and *GSTT1* status on the results. Collectively, these results clearly demonstrate that isothiocyanates, whether administered in pure form, as in the PEITC clinical trial, or in the form of a vegetable beverage, as in the broccoli sprouts clinical trial, can enhance detoxification of environmental toxicants and carcinogens. We also note that in the latter trial, exposure to benzene and acrolein was remarkably higher than in the U.S. because of significant levels of air pollution in the Shanghai area where the trial was performed. Collectively, these results strongly support our hypothesis that watercress consumption can enhance the detoxification of volatile organic carcinogens and toxicants, thus enhancing health by providing protection against the effects of environmental toxicants and carcinogens. Our results could significantly expand the armamentarium of cruciferous vegetables with demonstrated protective effects against carcinogens and toxicants.

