3.0 Study Endpoints/Events/Outcomes

The primary endpoint is to conduct a clinical trial with 350 subjects (both non-smokers and smokers) to determine the effects of the watercress preparation on detoxification of environmental toxicants and carcinogens.

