15.0 Statistical Considerations

Descriptive statistics will be used to summarize subject characteristics, for example subject demographics (age and gender, race, ethnicity, income, current occupation and usual occupation), medical history and current health status for current diagnoses, symptoms and past health problems. Categorical variables will be described by their frequencies and the continuous measurements will be described by their mean, median, range, and standard deviations. We will use paired *t*-test to compare distributions of continuous variables (e.g., age, number of cigarettes per day, number of pack-years of cigarettes smoked over lifetime) between the two treatment groups (watercress and placebo arms). The McNemar's Chi-squared test will be used to compare categorical variables, such as sex, *GSTM1* and *GSTT1* genotypes between the two treatment groups.

The statistical analysis section particularly focuses on Specific Aim 3, which investigates the hypothesis that detoxification of these noxious agents by conjugation with glutathione, as indicated by mercapturic acid levels in urine, will be significantly elevated compared to placebo in subjects who consumed the watercress preparation and are null for *GSTM1*, *GSTT1*, or both. We can test for a Period x Treatment interaction such as testing if the effect of the watercress preparation varies depending on whether it is given in the first period compared to the second period.

PROTOCOL TITLE: Watercress in Detoxification of Environmental Toxicants and

Carcinogens

VERSION DATE: July 23, 2020

We will have baseline measurements on each subject. Participants will be asked to attend clinic visits on days 0 (baseline), 2, 7 and 14 for each of the periods they are receiving product (watercress or placebo). We will compare the baseline measurements on the outcome variables and some important covariates between the two treatment groups through the two-sample t test to see if there is any significant difference between the two groups in order to ensure homogeneous treatment groups. We will also perform repeated data analysis using the measurements on each subject and consider different baseline parameters for the watercress and the placebo group in our multivariate regression analysis described later.

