Measurements: For the comparison between the two treatment groups, we will consider measurements excluding the baseline observation. Measurements will be taken from each subject in the two supplementation sequences as seen in the following diagram:

Group 1: Period #1 (watercress; A1) – washout – Period #2 (placebo; B2)

Group 2: Period #1 (placebo; B1) – washout – Period #2 (watercress A2)

The letter is used to denote supplementation (A for watercress and B for placebo) and the number, 1 or 2, denotes the period. We will assume, in the formulation of statistical models, that the measurements A1, A2, B1, and B2 are “normally distributed” in log-scale. These letters can represent one of our outcome variables: urinary mercapturic acid levels of specific toxicants (e.g. benzene, acrolein, crotonaldehyde, propylene oxide, etc.) or for mercapturic acids generally, or DNA adducts of acrolein.

Main Outcome Variables: Our data analysis will be based on the following “outcome variables”:

$$X1 = B2 - A1; \text{ and } X2 = B1 - A2.$$

This subtraction will cancel the “within-sequence” effects of all subject-specific factors, leaving only two to be modeled and analyzed: the Treatment (or Supplementation) effect and the Period (or Order) effect. The measurements will result in two independent samples. Each will have the same sample size if there are no dropouts or missing data. Otherwise the number of subjects for each group of measurements (i.e., X1 and X2) will differ if there are dropouts and missing data.

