We would obtain values of X1 or X2, which is a log of "ratio" for each subject in each of the two groups with different supplementation order, it's (watercress/placebo) for group 1 and (placebo/watercress) for group 2. We'll then compute the averages of these log ratios, i.e \bar{x}_1 and \bar{x}_2 . We will do this calculation separately for the double null group ($\hat{\alpha}_{nn}$), and single null group ($\hat{\alpha}_{np}$). We will compare this average ratio with the average ratio of the double positive group ($\hat{\alpha}_{pp}$). With the double nulls being about 15% of the population, *GSTM1* single nulls (45%) and *GSTT1* single nulls (23%), we expect to see 60 double nulls, 180 *GSTM1* single nulls, 92 *GSTT1* single nulls, and 68 double positive individuals. If there is no influence of *GSTM1* or *GSTT1*, the effect of watercress supplementation would be the same between the double null and the double positive group or between the single null and the double positive group. We will test for the significance of the genotypic effect by using a two-sample t test.

PROTOCOL TITLE: Watercress in Detoxification of Environmental Toxicants and

Carcinogens

VERSION DATE: July 23, 2020

In order to estimate the power for that comparison, we need information on the variability of mercapturic acid levels within and between subjects. We will compute the variances of each of these genotypic groups separately and then obtain a pooled variance estimate to compute our pooled t test statistic. Based on our previous work, we used an intra-subject CV of 0.4 and an inter-subject CV of 0.6, which translates to a pooled standard deviation of 0.657. According to Table 3, the percentage difference between the Placebo and PEITC groups with the double null genotypes varied from 29.8% to 95.4%, whereas the percentage difference for the double positive genotypes varied from 4% to 7%. In general, we will have 80% power to detect a difference of 35% between the double null and double positive group and given the range of difference between these two groups in Table 3, we expect to have good power to study this interaction between watercress and *GSTM1* or *GSTT1* genotypes.

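### Section 15.0 states no hypothesis test or power for watercress versus placebo, the question the trial asks; its stated t test and primary parameter are null under a uniform benefit

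*Combined protocol and SAP*

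**What the plan says.** **The question.** Section 1.0 hypothesises that watercress "will enhance the detoxification of multiple environmental toxicants and carcinogens", with a larger effect expected in *GSTM1* or *GSTT1* nulls. Section 3.0 gives the primary endpoint as a 350-subject trial "to determine the effects of the watercress preparation on detoxification of environmental toxicants and carcinogens", with no restriction by genotype. Section 15.0 says "The statistical analysis section particularly focuses on Specific Aim 3", whose hypothesis is that mercapturic acid levels "will be significantly elevated compared to placebo in subjects who consumed the watercress preparation" and who carry a null genotype. All three are comparisons with placebo.

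**The analysis.** Section 15.0 sets up a treatment comparison: "For the comparison between the two treatment groups, we will consider measurements excluding the baseline observation". It forms within-person differences X1 and X2 and says that treatment and period effects remain to be analysed. The tests it then states on the outcomes are:

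- average log ratios compared between genotype groups: "We will test for the significance of the genotypic effect by using a two-sample t test";
- in the mixed model, a test of association between genotype and each outcome;
- a t test of the interaction of treatment order (glossed as before versus after) with genotype group, named as the primary parameter;
- an option: "We can test for a Period x Treatment interaction".

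Supplementation is one of the independent variables in the mixed model. The only power statement is 80% for a 35% difference between double nulls and double positives.

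**The concern.** None of the stated tests has as its null hypothesis that watercress and placebo give the same mean level, in all participants or within a null group. Even the Aim 3 hypothesis, as worded, has no test attached. If watercress raised excretion by the same proportion in every genotype, the genotype t test and the primary parameter would both have true value zero.

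The protocol's own background supplies that scenario. In the broccoli-sprout trial, SPMA rose 61% and 3-HPMA 23%, "although there was no statistical effect of" *GSTM1* and *GSTT1* status. The sponsor's earlier PEITC trial, also in Section 2.0, did report both of the results missing here: an overall treatment effect (SPMA +24.6%, P=0.002; 3-HPMA +15.1%, P=0.005) and treatment effects within each genotype (Table 3, first footnote).

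At stake is the status of the main claim. A conclusion that watercress works would rest on a coefficient chosen after the fact, beside a primary parameter that may be non-significant for reasons unrelated to efficacy.

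**Working it through.** **Inputs from the documents.** Section 10.0: 350 needed, 400 enrolled, 15% attrition (400 × 0.85 = 340, so both 340 and 350 are used). Section 15.0: pooled SD 0.657, intra-subject CV 0.4, 60 double nulls (15%) and 68 double positives (17%) of 400. Section 15.0 states neither alpha nor sidedness; two-sided 0.05 is assumed.

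**1. The plan's own figure.** With 350 completers the groups are 52.5 and 59.5. Reading 35% as 0.35 on the log scale:

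- SE = 0.657 × √(1/52.5 + 1/59.5) = 0.1244
- power = Φ(0.35/0.1244 − 1.96) = 0.803

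The stated 80% is reproduced, and it belongs to the genotype contrast alone. (Read as ln 1.35, the power is 0.674.)

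**2. What the stated tests do under a uniform benefit.** In 20,000 simulated trials of 350 people, each log difference was drawn from a normal distribution with mean ln 1.20 and SD 0.657, the same for all genotypes. The genotype t test (52 v 60) rejected in 4.9% of trials, which is its alpha. A test of the overall mean difference rejected in over 99.9%. The order-by-genotype interaction is also zero here, whether order means period or product, as is the Period × Treatment term.

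**3. What an overall test could detect.** With balanced sequences, SE = SD/√N, and the detectable increase at 80% power is exp(2.80 × SD/√N) − 1. The documents give no SD for the within-person log difference, so a range is used:

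| SD of log difference | Source | N = 350 | N = 340 |
|---|---|---|---|
| 0.545 | assumed: √2 × √ln(1 + 0.4²) = √2 × 0.385 | 8.5% | 8.6% |
| 0.657 | the plan's pooled SD | 10.3% | 10.5% |
| 0.929 | assumed, pessimistic: √2 × 0.657 | 14.9% | 15.2% |

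For the earlier trial's 15.1% rise in 3-HPMA, power is 0.98 at SD 0.657 and 0.80 to 0.81 at SD 0.929. By contrast, the genotype comparison at 340 completers (51 v 58) needs about 34% (SD 0.545) to 42% (SD 0.657).

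**4. Within double nulls.** With 52.5 completers, exp(2.80 × SD/√52.5) − 1 gives 23.4% at 0.545, 28.9% at 0.657 and 43.2% at 0.929. Table 3 shows rises of 29.8% to 95.4% in that group.

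**5. Which contrast of X is the treatment effect.** Let τ be the log effect of watercress over placebo and π the shift from period 1 to period 2.

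- By the formulas in Section 15.0, both differences are placebo minus watercress: E(X1) = π − τ and E(X2) = −π − τ. Their average is −τ.
- By the next paragraph, the ratio is watercress over placebo in group 1 and placebo over watercress in group 2: E = τ − π and −τ − π. Their average is −π, and treatment cancels.

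The two descriptions conflict, so a reader cannot recover an implied treatment test from the text.

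**The case against.** The strongest reply is that the treatment effect is plainly meant to be analysed. Section 15.0 announces a comparison of the two treatments, names the treatment effect as one of two left to model, and sets up two independent samples as in a standard two-period crossover. Log ratios are averaged within genotype groups. The mixed model carries a supplementation term, the fallback GEE analysis and the non-linear models are to address watercress as well as genotype, and the smoking-subgroup paragraph discusses power for the watercress effect among double-null smokers. This stands as evidence of intent.

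It also rules out stronger readings. A reader might infer that the plan tests nothing but genotype differences; it also offers the Period × Treatment test, although that cannot show a uniform benefit. A reader might infer that a uniform benefit would be invisible or would have to be reported as a null trial; the supplementation coefficient and the group averages would show it. Nor do the documents support a claim that the trial is too small for the overall question.

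What the reply does not supply is a null hypothesis, alpha, detectable effect or decision rule for watercress versus placebo. The mixed model is described as a supplement to the t test, and its stated tests concern genotype and the interaction. Specific Aims 1 and 2 are not described in the text available, so an analysis attached to them cannot be excluded.

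**Conclusion.** The point holds as a gap in specification. The objective, the primary endpoint and the Aim 3 hypothesis ask about watercress versus placebo; Section 15.0 states no test or power for that effect, overall or within null genotypes, and the parameter it calls primary answers a different question. An estimate would exist, but not a prespecified confirmatory test.

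The planned sample could detect an overall rise of about 8.5% to 10.5%, or about 15% on the pessimistic SD. This rests on two-sided 0.05, 80% power, 340 to 350 completers, a single analyte without multiplicity adjustment, and SDs of which only 0.657 is the plan's own. The sponsor should correct this before analysis.

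**What to change.** In Section 15.0:

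1. Reconcile the definition of X. Define both sequence differences as log(watercress) minus log(placebo), so that a benefit is positive in each sequence.
2. Name as the first confirmatory analysis the period-adjusted watercress-versus-placebo effect in all participants: the product coefficient in the mixed model or, equivalently with complete data, the mean of the two sequence-specific differences.
3. Follow it with the same contrast within the null groups, and then with the product-by-genotype interaction in place of the order-by-genotype one.
4. State alpha, sidedness and the primary analyte(s); Table 1 lists eight mercapturic acids and each outcome is to be modelled separately.
5. Report ratios with 95% confidence intervals, and state the detectable effect for each step with the SD of the log difference that it assumes.

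The cost is SAP wording only. It uses data the protocol already collects and needs no more participants.

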Study design. Participants will be asked to attend clinic visits on days 0 (the day of product distribution), 4 (± 1 day), 7 (± 1 day) and 14 (± 1 day) for each of the periods they are receiving product and weekly during the 4 week washout between periods (see **Figure 2**). We use a 4-week washout period because the 1-week washout in our preliminary studies may not have been sufficient [11]. Each visit is composed of three parts and will be completed in a single day. Part 1: Prior to the clinic visit the participant will collect their first morning void urine. Part 2: In a virtual visit, participants will be asked to complete multiple online surveys (see **Table 4**). Part 3: Participants will drop off their first morning void urine (also used to test for pregnancy) at the research clinic (University of Minnesota – Tobacco Research Programs, [name]). Blood (once allowed), blood pressure, saliva, oral rinse, and buccal cells will be collected. After this collection, participants will be provided with either the watercress powder or the placebo and the flavoring product. Subjects will be given written instructions on how to add the watercress/placebo powder and flavor product to water and will also be provided a link to a video with instructions. They will be provided three different flavors from which they can sample. At the Day 4 visit, they will be asked to choose one of the flavors to be used during the rest of this phase. They will be asked to drink the formulation at breakfast, lunch and dinner. Participants will receive one jar of the FDWC on day 0 and the second jar on day 7. Participants will receive one jar of maltodextrin on day 0, which will last until the end of the study. A log will be kept of the products that are dispensed and any amounts unused. At the end of each two-week period (or end of study participation, whichever comes first), we will ask all participants to return any unused product. Compliance of use of the study products will be determined by the product accountability log and biochemical verification (e.g., urinary PEITC-NAC and total isothiocyanates). Participants will be provided standardized counseling about the importance of using the assigned products as directed and if procedural compliance is an issue, the research assistant will discuss the obstacles and develop a plan to overcome these obstacles. Participants will also be provided a urine collection cup, dietary intake log and dosing log at each visit.

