Biospecimen collection. All collection containers will be labeled with study number, subject number, collection date and type of biological sample (urine, blood, saliva, buccal cells). At each clinic visit, first morning void urine samples will be collected and participants will be asked to submit saliva and oral cells. Participants will be asked to brush their teeth in the bathroom at the beginning of the visit by using a provided commercial individually packed pre-pasted toothbrush (ReadyBrushTM) and asked to not eat, drink, smoke or chew gum for 5 min prior to obtaining oral cells. Saliva samples will be collected by asking the participant to spit in a sterilized 10 ml tube. These samples will be frozen at -20 °C for possible future oral microbiome studies. Oral cells will be collected by first, doing an oral rinse. Participants will squirt 15 mL of saline solution into their mouths and swish for 45 seconds. The oral rinse sample will be expectorated back into a 50 mL tube. After completing the rinse, participants will scrape the oral mucosa inside the mouth with a cytobrush. Two cytobrushes will be used on each subject to collect two separate samples from the left and the right inner cheek. After scraping the mucosal surface, each cytobrush will be immediately placed into a separate pre-labeled sterile polypropylene tube containing 5 mL of saline, swirled for a

PROTOCOL TITLE: Watercress in Detoxification of Environmental Toxicants and Carcinogens

VERSION DATE: July 23, 2020

few seconds, and tapped against the walls of the tube to ensure the cells are transferred from the brush to the saline. Oral cells will be stored at -20°C for DNA isolation and research in future years of this study, which may include analysis for protein expression, including GSTP1. The use of oral cells for protein expression studies has been described [70].

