Multivariate Regression Analysis: We will use multivariate regression analysis to supplement the t-test by pooling the data together and using each of the primary outcome variables as dependent variable, separately. In addition to the variables representing the supplementation, treatment order, and status of *GST (M1, T1)* genotypes, the list of independent variables will include socio-demographic characteristics such as gender, age, smoker vs non-smoker, baseline smoking level (cigarettes per day), and intake of dietary nutrients. We will fit a linear mixed-effect model where the dependency in the repeated measurements on each individual will be captured through a random effect. The status of *GST (M1, T1)* genotypes will be modeled as fixed-effects and we will test for the null hypothesis of no association between the genotypes and each outcome. Our primary parameter of interest will be the interaction between the treatment order (pre vs post) and the genotype groups (double null, *GSTM1* single null, *GSTT1* single null, and double positives). We will perform a t-test to assess the significance of the interaction parameter. The residual covariance structure should be selected among several candidates, i.e. autoregressive, compound symmetry, unstructured, etc., to estimate the fixed and random effects. We do not anticipate much missing data on the participants. In general, we will assume missingness at random (MAR) and the likelihood-based linear mixed effect model will provide consistent estimates of our parameters of interest in presence of MAR. The models will be assessed through their Akaike's Information Criterion and Bayesian's Information Criterion. The normality of the outcome variables will be assessed and in presence of non-normality, we will also implement Generalized Estimating Equations to study the impact of watercress and genotypes on each outcome variable. We will use the statistical software R packages nlm and gee to perform the above analysis. These packages will also provide the flexibility to fit non-linear mixed effect models to assess the impact of watercress and genotype groups.

PROTOCOL TITLE: Watercress in Detoxification of Environmental Toxicants and Carcinogens

VERSION DATE: July 23, 2020

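### The treatment comparison leaves out the pre-product day-0 values from both periods, so the trial may forgo precision that adjustment could give at almost no cost; the size of the gain is unknown

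*Combined protocol and SAP*

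**What the plan says.** Collection (section 5.0). The schedule reads: "Participants will be asked to attend clinic visits on days 0 (the day of product distribution), 4", followed by days 7 and 14, in each product period. On urine: "At each clinic visit, first morning void urine samples will be collected". Table 4 also marks the first urine void for the product-use visits, day 0 included. On the order of events at the visit: "After this collection, participants will be provided with either the watercress powder or the placebo". Each period therefore has a pre-product biomarker value.

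Main comparison (section 15.0, Measurements and Main Outcome Variables). The plan states "We will have baseline measurements on each subject", but for comparing treatments "we will consider measurements excluding the baseline observation". The outcomes are X1 = B2 − A1 and X2 = B1 − A2 on the log scale. The plan says this subtraction cancels the within-sequence "effects of all subject-specific factors, leaving only two to be modeled and analyzed", namely treatment and period. It does not say which on-product visit, or what average of visits, A and B stand for.

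Supplementary regression (section 15.0). The plan will "consider different baseline parameters for the watercress and the placebo group in our multivariate regression analysis described later". The later covariate list covers supplementation, treatment order, genotype, gender, age and smoker status, and ends with "baseline smoking level (cigarettes per day), and intake of dietary nutrients". No day-0 mercapturic acid value is in it. The regression is described as a supplement to the t-test.

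**The concern.** Subtracting one period from the other removes whatever is constant in a person. It does not remove what changes in that person between periods. The two day-0 visits are about six weeks apart (14 days of product plus a 4-week washout), while each is at most about two weeks from the on-product visits of its own period. The biomarkers follow exposure through diet, air and smoking, so some variation shared within a period is plausible. Any such drift is noise in the watercress-placebo log ratio, and the difference between the two day-0 values carries information about it.

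The listed covariates do not do this job: gender, smoker status and baseline cigarettes per day are the same in both periods and have no main effect on a within-person difference. At stake is the width of the interval for the treatment effect and for the genotype contrast, which rests on an expected 60 double nulls and 68 double positives out of 400 enrolled.

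**Working it through.** **The plan's own figure.** Section 15.0 claims 80% power for a 35% difference between double nulls and double positives with SD 0.657. Alpha is not stated; I assume two-sided 0.05. Scaling 60 and 68 from 400 enrolled to the 350 needed (section 10.0) gives 52.5 and 59.5.

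- SE = 0.657 × √(1/52.5 + 1/59.5) = 0.124
- 0.35 / 0.124 = 2.81, and 2.81 − 1.96 = 0.85, so power is 80.3%. The figure reproduces.
- Degrees of freedom: 52.5 + 59.5 − 2 = 110.

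**What the crossover has already removed.** The intra-subject CV of 0.4 gives a within-person log variance v = ln(1.16) = 0.148. With one value per period, Var(X) = 2v = 0.297 and SD(X) = 0.545; the between-person part has cancelled. With SD 0.545 and the same 350 completers, power is 92.4% for a difference of 0.35, or 82.9% if 35% is read as ln 1.35, before any use of baseline.

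**What day-0 adjustment can add.** Write each log value as a person effect, plus a participant-by-period effect with variance f·v, plus a visit effect with variance (1 − f)·v. Let D be the within-person difference of the two day-0 values, signed like X.

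- Var(D) = 2v and Cov(D, X) = 2f·v.
- One on-product visit: Var(X) = 2v, so r = f and adjustment multiplies Var(X) by 1 − f².
- Mean of three visits: Var(X) = 2v·[f + (1 − f)/3], so the proportional cut is f² / [f + (1 − f)/3].
- Change from baseline, one visit: Var(X − D) = 2v·2(1 − f), so the multiplier is 2(1 − f).

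The documents do not give f. The plan's two CVs contain no participant-by-period component, so they neither support nor exclude any value. The range below is an assumption.

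| f | Cut, one visit | Cut, mean of three | Power, adjusted, one visit (SD 0.657) | Same (SD 0.545) | Power, change score, one visit (SD 0.657) |
|---|---|---|---|---|---|
| 0 | 0% | 0% | 80.3% | 92.4% | 51.2% |
| 0.1 | 1% | 2.5% | 80.7% | 92.6% | 55.4% |
| 0.2 | 4% | 8.6% | 81.9% | 93.4% | 60.4% |
| 0.3 | 9% | 16.9% | 83.9% | 94.5% | 66.2% |
| 0.5 | 25% | 37.5% | 90.1% | 97.5% | 80.3% |

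Power is for 350 completers and a difference of 0.35. Simulation at f = 0, 0.2, 0.4 and 0.6 agreed with the variance formulas. With the mean of three visits and f = 0, a change score raised the variance from 0.099 to 0.397.

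**Why these cuts are upper bounds.** The model takes day 0 to be as strongly related to day 14 as to day 4. It also allows no person-to-person variation in response, which would enter X but not D. Either departure lowers r².

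**The case against.** The strongest reply is that this is a crossover. The large gain that baseline adjustment brings in a parallel-group trial comes from stable differences between people, and X has already removed those. Carrying the person-level correlation implied by the CVs, 0.307/(0.148 + 0.307) = 0.67, over to X would count that gain twice. This stands: only the within-period share f is left to recover, and it may be small or nil.

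Second, a reader might infer that the plan ignores baseline altogether. The documents do not support that. Section 15.0 promises a repeated-measures analysis and says baseline parameters will be considered in the regression. Day-0 values modelled as repeated outcomes would not appear in a covariate list, and the interaction described there as pre versus post could be read as including pre-product observations. What stands is that the wording commits to no particular use, and that the main X comparison plainly leaves day 0 out.

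Third, the two day-0 values may not be like for like. The period-2 value follows the first product period, and section 5.0 says the 1-week washout of the preliminary studies may not have been long enough. Participants are asked at screening to avoid cruciferous vegetables, with no stated run-in, so the period-1 value may reflect recent intake while the period-2 value follows about six weeks of requested abstinence. This stands: the day-0 difference is an imperfect measure of drift, and an unadjusted result should be shown beside the adjusted one.

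**Conclusion.** The point holds as a possible gain in efficiency. Pre-product values exist for both periods, the main comparison excludes them, and the regression does not clearly use them. Adjustment would cut the variance of X by at most about 1% to 4% if f is 0.1 to 0.2, 9% at 0.3 and 25% at 0.5 with one on-product visit, and by more with the mean of three. If f is zero, the price is one degree of freedom out of about 110 in the double-null versus double-positive test.

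A reader might infer a demonstrated loss of precision or a shortfall in power. The documents do not support that: f is not reported, and the stated 80% reproduces without baseline. Nor does leaving out day 0 by itself bias the planned comparison. The omission and the formulas are secure; the size of the benefit is not. The change is worth making because it is nearly free, and because settling the use of baseline now rules out a poor choice, such as a change score, once data are seen.

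**What to change.** In section 15.0:

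1. Add the within-person difference of the two day-0 log values as a covariate in the analysis of X, including the genotype contrast, alongside the treatment and period effects the section already intends to model. Sign it the same way as X. As X1 and X2 are defined, that is day 0 before placebo minus day 0 before watercress. State the sign explicitly, because the later text describes the ratio as watercress/placebo in group 1 and placebo/watercress in group 2.
2. In the mixed model, include each period's day-0 value together with the participant's mean day-0 value. The mean is needed because raw day-0 levels differ by genotype: in Table 2, SPMA is 0.44 in double nulls and 3.56 in double positives, about eightfold. A single day-0 term would mix that difference with drift.
3. Adjust; do not subtract. With one on-product visit, a change score loses precision unless the correlation between the day-0 and on-product differences exceeds 0.5.
4. State which on-product visit or average A and B represent.
5. Report the unadjusted X analysis as a sensitivity result, because of possible carry-over in the period-2 day-0 value and recent cruciferous intake in the period-1 value.

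The cost is a few lines of text and one degree of freedom in the X analysis. Day-0 urine is already collected, so no new visit or sample is needed.
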